8.4 Pharmacokinetics

Sparse blood sampling for APR-246 pharmacokinetic (PK) measurements will be performed from all patients in Arm A at days 1, 2 and 4 in Cycle 1 (Table 16).

Please refer to the laboratory manual for detail instructions on processing of the pharmacokinetic samples.

Table 16: Sparse PK Blood Sampling Time Points for APR-246 in Cycle 1 (Arm A)

Day 1	Before infusion	0-2 h prior APR-246 infusion (nominal time point 0 h)
	At end of rapid phase	45 min (at the end of first part of infusion) (nominal time point 0.75 h)
	At end of infusion	± 5 min relative to the end of infusion (nominal time point 6 h)
	After infusion	30-60 min AFTER infusion (nominal time point 7 h)
Day 2	Before infusion	0-2 h prior APR-246 infusion (nominal time point 24 h)
Day 4	Before infusion	0-2 h prior APR-246 infusion (nominal time point 0 h)
	At end of rapid phase	45 min (at the end of first part of infusion) (nominal time point 0.75 h)
	At end of infusion	± 5 min relative to the end of infusion (nominal time point 6 h)
	After infusion	30-60 min AFTER infusion (nominal time point 7 h)

8.5 Pharmacodynamics

8.5.1 Optional Tumor Biopsy

Archived tumor tissue (FFPE sections) from all patients will be reviewed by a gynecological pathologist to confirm the diagnosis of high grade serous ovarian cancer, and positive IHC staining for p53. In addition, these samples will be used to determine p53 status by a central laboratory.

Additional analysis may include biomarkers and evaluation of tumor cell DNA.

Optional paired tumor biopsies will be collected in Arm A: one prior to treatment and the other during treatment (optimally within the last 30 minutes of the APR-246 infusion on day 3 of the first cycle, however a biopsy obtained at the end of the APR-246 infusion on day 2 is acceptable). For Arm B, one tumor biopsy to be performed prior to chemotherapy.

Two tumor cores will be taken at each biopsy, one will be flash frozen and one will be formalin fixed.

The choice of the tumor lesion is at the Investigator's discretion. If either tumor biopsy fails, the patient can still be included in the trial. The reasons for failure to obtain a biopsy must be recorded in the eCRF. If the pre-treatment tumor biopsy is not obtained, no further tumor biopsies will be attempted.

Any lesion that is used for biopsy purposes should be recorded as a non-target lesion only.

The following assessments may be performed by Aprea Therapeutics AB or a central laboratory appointed by Aprea Therapeutics AB (please refer to Laboratory Manual).

- Immunohistochemistry for tumor cellularity and p53 protein staining and other IHC markers (i.e. BRCA1, ER stress markers)
- RNA/DNA extraction for microarray tumor gene expression profiling
- Proteomics - Lysates for reverse phase proteomics

Specimens may be stored for future evaluation of APR-246 in target tissue.

The quality and quantity of the biopsy will determine which analyses are to be performed. The mutational analyses will be done in batches and the results will not be reported to the trial site during the treatment period.

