4.0 STUDY DESIGN

4.1 Overview of Study Design

This study is an open-label, multi-center Phase II proof-of-concept study with a dose confirmation component to assess whether patients with platinum sensitive recurrent TP53 mutated high grade serous ovarian cancer (HGSOC) will benefit from treatment with APR-246 in combination with a carboplatin/PLD chemotherapy regimen. It is planned that patients will receive up to 6 cycles of treatment.

Archived sections from the original tumor sample will be reviewed by a gynecological pathologist to confirm the diagnosis of HGSOC and positive IHC staining for p53 (please refer to the laboratory manual). Patients without positive p53 staining will not be included.

Patients will be randomly assigned in a 1:1 ratio to receive either:

- Arm A: APR-246 with the carboplatin/PLD chemotherapy regimen,
- Arm B: Carboplatin/PLD chemotherapy alone.

Optional frozen/fixed core biopsies will be undertaken after randomization, but prior to any infusion, on day 1 for all patients and day 3 in APR-246 patients.

The study will enroll up to 400 patients with positive IHC staining for p53. A CT scan/MRI using RECIST v1.1 criteria will be performed at pre-treatment, after 2 cycles (8 weeks), 4 cycles (16 weeks) and after the last cycle (24 weeks).

At subsequent follow-up visits, tumor assessments by CT scan/MRI will be performed 2 months (\pm 2 weeks) after the end of treatment visit and every 3 months (\pm 2 weeks) thereafter, until the documented disease progression, as determined by the Investigator at each site and defined by RECIST v1.1.

All scans for each individual patient should have the same modality (CT or MRI) but CT is preferred.

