5.0 SELECTION AND WITHDRAWAL OF PATIENTS

5.1 Inclusion Criteria

To be eligible to participate in this study, patients must meet all of the following inclusion criteria:

1. Archived sections from the original FFPE sample reviewed by a gynecological pathologist confirming High Grade Serous Ovarian Cancer, High Grade Serous Peritoneal Cancer or Primary Fallopian Tube Cancer, and positive IHC staining for p53 assessed according to defined standard (as detailed in the laboratory manual). Cases that do not show p53 staining will not be included.
2. Radiologically-confirmed Disease Progression between six and twenty-four (6-24) months after a first or second platinum based regimen.
3. At least a single (RECIST v1.1) measurable lesion.
4. Adequate organ function prior to registration:
 - a) Bone Marrow Reserve:
 - Absolute neutrophil count (ANC) $\geq 1.5 \times 10^9/L$,
 - Platelets $\geq 100 \times 10^9/L$,
 - Hemoglobin $\geq 9 \text{ g/dL}$.
 - b) Hepatic:
 - Total bilirubin level $< 1.5 \times \text{ULN}$,
 - ALT and AST $< 2.5 \times \text{ULN}$.
 - c) Renal:
 - Calculated creatinine clearance $> 30 \text{ mL/min}$.
 - d) Electrolytes
 - Potassium within institutional normal ranges.
5. Toxicities from previous cancer therapies, excluding alopecia, must have recovered to grade 1 (defined by CTCAE version 4.0). Chronic stable grade 2 peripheral neuropathy secondary to neurotoxicity from prior therapies may be considered on a case by case basis by the Principal Investigator.
6. If of childbearing potential, negative pre-treatment serum pregnancy test.
7. If of childbearing potential, willing to use an effective form of contraception (see below) during chemotherapy treatment and for at least six months thereafter.

Such methods include: (if using hormonal contraception this method must be supplemented with a barrier method, preferably male condom).

- Combined (estrogen and progestogen containing) hormonal contraception associated with inhibition of ovulation:
 - Oral
 - Intravaginal

- Transdermal
- Progestogen-only hormonal contraception associated with inhibition of ovulation:
 - Oral
 - Injectable
 - Implantable
- Intrauterine device (IUD)
- Intrauterine hormone-releasing system (IUS)
- Bilateral tubal occlusion
- Vasectomized partner

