7.2.3 Randomization

- **Randomization:** Optimally performed prior to any biopsy. See Section 4.4 for procedure.
- **Tumor biopsy (optional):** Arm A tumor biopsy to be performed within 28 days prior to cycle 1 day 1 APR-246 infusion. Arm B tumor biopsy to be performed within 28 days prior to cycle 1 chemotherapy administration.

7.2.4 All Cycles, Days 1 - 28

Day 1 examinations marked * do not need to be repeated if already performed within 3 days prior to day 1 cycle 1.

- **Medical history:** Only cycle 1*.
- **QoL questionnaires:** To be completed at each radiological tumor assessment time point.
- **Tumor Assessments:** CT scan/MRI at the end of cycle 2 (within 7 days prior to the start of cycle 3) and at the end of cycle 4 (within 7 days prior to the start of cycle 5).
- **Physical examination:** Day 1*. Height, weight, body surface area, and description of external signs of cancer.
- **ECOG performance status:** Day 1.
- **Vital signs:** Arm A on Days 1, 2, 3 and 4. Arm B only on Day 1. Heart rate, blood pressure, respiratory rate and temperature.
- **Hematology:** Day 1* (repeat to follow up on AEs as appropriate). Hemoglobin, hematocrit, MCV, platelet count, WBC and WBC differentials.
- **Coagulation:** Day 1*. INR and APTT, if patient is receiving warfarin assessments should be done weekly.
- **Blood chemistry:** Day 1*. (repeat to follow up on AEs as appropriate). Sodium, potassium, calcium, magnesium, chloride, glucose, creatinine, total bilirubin, aspartate transaminase [AST], alanine transaminase [ALT], urea, total protein, albumin, lactic dehydrogenase [LDH], direct bilirubin and uric acid.
- **CA-125:** Day 1*
- **Urinalysis:** Day 1*. Dipstick for protein, glucose, bilirubin and blood (perform microscopy if more than one positive dipstick test).
- **LVEF:** Assessed by echocardiography between day 21 of cycle 2 and start of cycle 3, and day 21 of cycle 4 and start of cycle 5. LVEF is mandatory before each additional

administration of PLD that exceeds a lifetime cumulative anthracycline dose of 450 mg/m². Additional echocardiograms can be conducted if clinically indicated per institutional practices.

- **Tumor biopsy (optional):** Arm A only. One tumor biopsy to be performed optimally at the end of APR-246 infusion on day 3 of the first cycle, however a biopsy obtained at the end of the APR-246 infusion on day 2 is acceptable. Refer to laboratory manual for detailed instructions.

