8.3.2.2 Evaluation of Best Overall Response by RECIST v1.1

The best overall response is the best response recorded from the start of the treatment until disease progression/recurrence (taking as reference for progressive disease the smallest measurements recorded since the treatment started). The patient’s best overall response assignment will depend on findings of both target and non-target disease and will also take into consideration the appearance of new lesions.

It is assumed that at each protocol-specified time point, a response assessment occurs. Table 11 provides a summary of the overall response status calculation at each time point for patients who have measurable disease at pre-treatment. When patients have non-measurable disease, Table 12 should be used.

Table 11. Time Point Response: Patients with Target (+/- non-target) Disease

Target Lesions	Non-target Lesions	New Lesions	Overall Response
CR	CR	No	CR
CR	Non-CR / non-PD	No	PR
CR	Not evaluated	No	PR
PR	Non-PD or not all evaluated	No	PR
SD	Non-PD or not all evaluated	No	SD
Not all evaluated	Non-PD	No	NE
PD	Any	Yes or No	PD
Any	PD	Yes or No	PD
Any	Any	Yes	PD

CR=complete response, PR=partial response, SD=stable disease
PD=progressive disease, NE=inevaluable

Table 12. Time Point Response: Patients with Non-target Disease Only

Non-target Lesions	New Lesions	Overall Response
CR	No	CR
Non-CR / non-PD	No	Non-CR / non-PD*
Not all evaluated	No	NE
Unequivocal PD	Yes or No	PD
Any	Yes	PD

CR=complete response; PD=progressive disease; NE=inevaluable
* Non-CR/non-PD is preferred over SD for non-target disease

Best response determination for studies where confirmation of CR or PR is required: Complete or partial responses may be claimed only if the criteria for each are confirmed by a repeat assessment at least 4 weeks later. In this circumstance, the best overall response can be interpreted as in Table 13.

Table 13. Best Overall Response when Confirmation of CR and PR is Required

Overall response First time point	Overall response Subsequent time point	BEST overall response
CR	CR	CR
CR	PR	SD, PD or PR*
CR	SD	SD provided minimum criteria for SD duration met, otherwise PD
CR	PD	SD provided minimum criteria for SD duration met, otherwise PD
CR	NE	SD provided minimum criteria for SD duration met, otherwise NE
PR	CR	PR
PR	PR	PR
PR	SD	SD
PR	PD	SD provided minimum criteria for SD duration met, otherwise PD
PR	NE	SD provided minimum criteria for SD duration met, otherwise NE
NE	NE	NE

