9.4 Analysis Populations

All randomized subjects will be analyzed according to the group in which they were randomized.

Intent-to-Treat (ITT): All randomized patients will be included in the intent-to-treat (ITT) population. The ITT population will serve as the primary analysis population for efficacy.

Safety Evaluable Population: All randomized patients who received any amount of study medication (APR-246, carboplatin, or PLD) will be considered evaluable for safety, regardless of the duration of treatment. This population will be used to summarize all safety parameters.

Efficacy Evaluable Population: All randomized patients with pre-treatment measurable disease by RECIST v1.1 who have at least one radiographic assessment after pre-treatment or discontinue study medication early due to disease progression and have a TP53 mutation will be considered evaluable for efficacy. The efficacy-evaluable population will be the secondary analysis population for efficacy.

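### Section 8.5.1 turns any biopsied lesion into a non-target lesion without protecting a sole measurable lesion, so an eligible patient can be left with no target lesion after randomisation

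*Combined protocol and SAP*

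**What the plan says.** Section 8.5.1 of the protocol sets two rules for the optional biopsies. On selection: "The choice of the tumor lesion is at the Investigator's discretion". On the consequence: "Any lesion that is used for biopsy purposes should be recorded as a non-target lesion only". Neither rule has an exception.

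The entry requirement in section 5.1, criterion 3, is "At least a single (RECIST v1.1) measurable lesion". Section 8.1.3 asks that all measurable lesions, up to two per organ and five in total, be recorded as targets at pre-treatment. It does not mention biopsied lesions.

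On timing, section 4.1 says "Optional frozen/fixed core biopsies will be undertaken after randomization, but prior to any infusion, on day 1 for all patients", and the synopsis agrees. Section 7.2.3 is softer about randomisation: "Optimally performed prior to any biopsy". Section 4.4 says treatment is not blinded. By arm, section 8.5.1 says "Optional paired tumor biopsies will be collected in Arm A: one prior to treatment and the other during treatment"; the second biopsy is ideally on day 3 of cycle 1, with day 2 acceptable. Arm B has one biopsy, before chemotherapy.

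**The concern.** Each rule is reasonable alone. Together they let a patient who qualified on one measurable lesion lose it as a target through an optional procedure done after her treatment arm is known. Nothing in the protocol requires a second measurable lesion before biopsy, bars biopsy of the only one, or says how such a patient is to be assessed.

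At stake is the uniformity of the RECIST measurement. Where the rule is applied, such a patient has no sum of diameters, so shrinkage cannot be scored as partial response and growth cannot be scored by the 20% criterion. A second route exists only in Arm A: no text requires the on-treatment biopsy to use the same lesion as the first, so it could reclassify a lesion already recorded as a target at baseline.

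**Working it through.** The plan states no figure on this point, so there is none to reproduce. The check sets the rules side by side and then sizes the effect under assumptions.

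**Step 1: what remains without a target lesion.**

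| Outcome | Rule | Available with no target lesion? |
|---|---|---|
| Partial response (RECIST) | 8.3.1: 30% fall in the target sum | No |
| Progression by growth of the target sum | 8.3.1: 20% rise and at least 5 mm | No |
| Complete response | 8.3.2 and Table 12 | Yes |
| Progression by new lesion | 8.3.2, 8.3.2.1, Table 12 | Yes |
| Unequivocal non-target progression | 8.3.2, Table 12 | Yes |

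**Step 2: which response table applies.** The text of section 8.3.2.2 assigns tables by measurability: Table 11 for patients with measurable disease at pre-treatment, Table 12 for non-measurable disease. By that text an eligible patient belongs to Table 11. But every Table 11 row leading to CR, PR or SD needs a target-lesion result, which she does not have. The title "Table 12. Time Point Response: Patients with Non-target Disease Only" describes her, but the sentence assigning that table does not. The plan leaves this open.

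**Step 3: the second route in Arm A.** Section 8.1.3 records targets at pre-treatment. The Arm A on-treatment biopsy comes later, the lesion is the investigator's choice, and the non-target rule covers any biopsied lesion. A recorded target can therefore be reclassified after baseline. Section 8.5.1 attempts no further biopsy if the pre-treatment one was not obtained, so this route can add lesions but not newly biopsied patients.

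**Step 4: size of the first route.** The documents give none of these shares; all are assumed:
- m, share with exactly one measurable lesion: 10-30%
- b, share biopsied: 10-50%
- q, chance that the biopsied lesion is the sole measurable one: 50-100%

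Affected share f = m × b × q; patients affected = 400 × f, using the maximum enrolment in section 9.3.

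| | m | b | q | f | of 400 |
|---|---|---|---|---|---|
| Low | 0.10 | 0.10 | 0.5 | 0.005 | 2 |
| Middle | 0.20 | 0.30 | 0.5 | 0.030 | 12 |
| Middle | 0.20 | 0.30 | 1.0 | 0.060 | 24 |
| High | 0.30 | 0.50 | 1.0 | 0.150 | 60 |

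The factor q matters because non-measurable lesions are not barred from biopsy.

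**Step 5: effect on the observed RECIST response rate.** Assume a true rate of 60%, made up of 10% CR and 50% PR. Assume also that affected patients keep CR, as Table 12 allows, and lose only PR. Then observed rate = (1 − f) × 0.60 + f × 0.10 = 0.60 − 0.50f.
- Low: 0.60 − 0.50 × 0.005 = 59.75%
- Middle: 0.60 − 0.50 × 0.030 = 58.5%, and 0.60 − 0.50 × 0.060 = 57.0%
- High: 0.60 − 0.50 × 0.150 = 52.5%

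The loss is 0.25 to 7.5 percentage points.

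**The case against.** The best defence is that 8.1.3 and 8.5.1 can be read together: all measurable lesions up to the cap are targets and biopsied lesions are non-target, so biopsies should go to lesions that are not targets. That is a sensible reading, but neither section states it, and 8.5.1 gives the investigator free choice. Biopsy is also optional, and only patients with a single measurable lesion are exposed to the first route. That limits the size but leaves the gap.

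The objection does succeed against four stronger conclusions that a reader might draw.

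- *Such patients leave the efficacy-evaluable population.* Section 9.4 asks for "All randomized patients with pre-treatment measurable disease by RECIST v1.1", not for a target lesion. Section 8.1.1 defines measurability by size and technique, and measurable lesions beyond the cap in 8.1.3 are also non-target. A biopsied lesion of sufficient size still met the definition at pre-treatment. This population is in any case secondary to ITT.
- *The maximum response rate falls by the affected share.* Table 12 keeps CR, so PR is what is lost. A CA-125 response under the GCIG criteria also remains possible for evaluable patients.
- *The central readers are not told which lesion was biopsied, so the primary endpoint is compromised.* Section 8.0 refers to a Radiology Manual for details of central reading, and that manual is not among the documents. A reader who was not told could also keep the lesion as a target, and the 20% criterion would still apply to centrally read PFS.
- *Biopsy uptake differs by arm.* Both arms are offered the same pre-treatment biopsy, and Arm A's second one follows only if the first was obtained. The documents show a different number of biopsies per patient, not different uptake.

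On timing, 7.2.3 allows some biopsies before randomisation, although 4.1 and the synopsis place them after it. The gap exists either way.

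**Conclusion.** The concern holds as a minor but real inconsistency. Following 8.5.1 as written can leave an eligible patient without a target lesion, and so without RECIST partial response or progression by growth of the target sum, in any reading that applies the rule. The response table for her is unclear. In Arm A alone, the on-treatment biopsy could also reclassify a recorded target.

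The frequency cannot be derived from the documents. The range of 0.5-15% of patients (2-60 of 400) rests wholly on the assumed shares. The loss of 0.25-7.5 points in response rate also needs the assumed 60% rate with 10% CR, and Table 12 as the governing table. These figures illustrate scale only. PFS can still be assessed for these patients. Whether centrally read PFS changes at all depends on instructions to the readers that are not available here, and no direction of bias between arms is shown.

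**What to change.** Reconcile section 8.5.1 with section 8.1.3 by stating that:

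- an optional biopsy is taken only when at least one other measurable lesion remains as a target lesion;
- no lesion recorded as a target is biopsied, including at the Arm A on-treatment biopsy;
- the site of the biopsied lesion is recorded for the baseline read, and section 8.1.3 excepts that lesion from the rule that all measurable lesions up to the cap are targets.

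With this in place every biopsied patient keeps a target lesion and Table 11 applies without ambiguity. The cost is a short text change and a few fewer optional exploratory biopsies, mainly in patients with a single measurable lesion.

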8.6 Exploratory Biomarker Research

Serum, plasma, whole blood and tumor samples will be collected from all patients and stored for retrospective exploratory analyses. These analyses may include (but are not necessarily limited to):

- Predictive markers of efficacy, tolerability and clinical pharmacology
- Biomarkers of acquired or innate resistance to APR-246
- Circulating free tumor DNA

The results of the exploratory biomarker research will be reported separately and will not be part of the Clinical Study Report.

A blood sample will be taken pre-treatment for collection of germ line DNA in order to allow comparison of germ-line and tumor cell DNA sequence.

The results of exploratory biomarker research may be pooled with data from other studies with APR-246 to generate hypotheses to be tested in future studies.

8.7 Biological Sample Handling

Details of sample collection, processing, shipping and storage will be described in the Laboratory Manual. Each sample for exploratory research will be identified with the study number and patient enrolment number. In this way exploratory biomarker and genetic data may be correlated with clinical data. Samples will be destroyed in the case of withdrawal of consent and regulatory audit enabled. Where genetic analysis will be undertaken the processes adopted for the coding and storage of samples will be more stringent in order to maintain patient confidentiality. As an added precaution, irrespective of the type of sample, the DNA sample will be assigned a unique number replacing the information on the sample tube. Thereafter, the DNA sample will be identifiable by the unique DNA number only. The DNA number will be used to identify the sample and corresponding data at the Aprea Therapeutics AB's designated contract laboratory. No personal details identifying the individual will be available to any person (Aprea Therapeutics AB or contract laboratory staff) working with the DNA. The samples and data for genetic analysis in this study will be single coded. The link between the patient enrolment code and the DNA number will be maintained and stored in a secure environment, with restricted access. The link will be used to identify the relevant DNA samples for analysis, facilitate correlation of genotypic results with clinical data, allow regulatory audit and to trace samples for destruction in the case of withdrawal of consent when the patient has requested disposal/destruction of collected samples not yet analyzed.

